Clinical Study Protocol: MCP-103-205

Amendment 1, 29 January 2019

Study Title:	A Phase 2, Randomized, Double-blind, Placebo-controlled, Parallel-group, Dose-range-finding Study of MD-7246 Administered Orally for 12 Weeks to Treat Abdominal Pain in Patients with Diarrhea-predominant Irritable Bowel Syndrome
Study Number:	MCP-103-205
Study Phase:	2
Product Name:	MD-7246
Indication:	Abdominal Pain in Diarrhea-predominant Irritable Bowel Syndrome
Investigators:	Multicenter
Sponsor:	Ironwood Pharmaceuticals, Inc. [name]
Medical Monitor:	██████████

	Date
Original Protocol:	11 October 2018
Amendment #1:	29 January 2019

Confidentiality Statement

The contents of this document are confidential and belong to Ironwood Pharmaceuticals, Inc. Except as may be otherwise agreed to in writing, by accepting or reviewing these materials, you (including any colleagues or subordinates) agree to hold such information in confidence and not to disclose it to others (except where required by applicable law), nor to use it for unauthorized purposes. In the event of actual or suspected breach of this obligation, Ironwood should be promptly notified.

SAE Reporting Fax Number/Email:

Organization	Email	Safety Hotline Fax	Safety Hotline Phone
PPD	[REDACTED]	[REDACTED]	[REDACTED]

Note: The preferred method of SAE reporting is via the electronic data capture (EDC) system; reporting should be done via fax/email if the EDC system is not available.

Sponsor Signatory:

[figure not shown]
[REDACTED]
[REDACTED]

Refer to the [final page](#) of this protocol for electronic signature and date of approval.

SYNOPSIS

Study Number: MCP-103-205
Study Title: A Phase 2, Randomized, Double-blind, Placebo-controlled, Parallel-group, Dose-range-finding Study of MD-7246 Administered Orally for 12 Weeks to Treat Abdominal Pain in Patients with Diarrhea-predominant Irritable Bowel Syndrome
Study Centers: Approximately 80 in the United States
Development Phase: 2
Objective(s): The objectives of this study are to evaluate the safety and tolerability, treatment effect on abdominal pain, and dose response of MD-7246 administered orally to patients with diarrhea-predominant irritable bowel syndrome (IBS-D). An exploratory objective of the study is to assess bowel function changes with MD-7246 in patients with IBS-D.

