4. STUDY OBJECTIVES

[figure not shown]
The objectives of this study are to evaluate the safety and tolerability, treatment effect on abdominal pain, and dose response of MD-7246 administered orally to patients with diarrhea-predominant irritable bowel syndrome (IBS-D). An exploratory objective of the study is to assess bowel function changes with MD-7246 in patients with IBS-D.

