7.4 SELECTION OF DOSAGE IN THE STUDY

This protocol is intended to evaluate the safety and tolerability, treatment effect on abdominal pain, and dose response of MD-7246 (previously referred to as linaclotide DR2) in IBS-D patients. The doses of MD-7246 were selected based on safety and tolerability results from prior clinical experience with this DR formulation of linaclotide and nonclinical pharmacology models of visceral pain.

In the Phase 1 PK/pharmacodynamic (PD) study MCP-103-105, linaclotide DR2 was well tolerated by 18 healthy subjects when administered for 7 days at doses of 300, 1200, and 3000 µg per day (6 subjects at each dose); AEs for linaclotide DR2 subjects were similar to placebo and all AEs were mild in severity. The 300-µg dose was also well tolerated in 2 prior clinical studies: as a single dose in 16 healthy subjects in the Phase 1 PK and food effect study MCP-103-104, and as chronic dosing (once daily for 12 weeks) in 66 IBS-C patients in the Phase 2b study MCP-103-204.

Linaclotide binds the GC-C receptor on human intestinal epithelial cell lines (T84 cells) at both high-affinity (K_{i1} of 1.23 nM) and low-affinity (K_{i2} of 156 nM) sites with high specificity. Binding of linaclotide to human intestinal (T84) cells stimulates cGMP production in a concentration-dependent manner, with a half maximal effective concentration (EC_{50}) of about 100 nM. A dose of 300 µg of linaclotide administered to the colon in humans will result in localized concentrations 2- to 10-fold the EC_{50} of linaclotide. Efficacy was observed on non-clinical models of visceral hypersensitivity at doses of 2.5 µg/kg, which is a human equivalent of approximately 300 µg.

The 600-µg and 1200-µg doses of MD-7246 were selected as incremental steps from the 300-µg dose to allow for evaluation of dose response in efficacy. Based on the safety and tolerability at doses up to 3000 µg in healthy subjects, the planned MD-7246 doses of 300, 600, and 1200 µg are expected to be safe and well tolerated in IBS-D patients.

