2. STUDY OBJECTIVES

The objectives of this study are to evaluate the safety and tolerability, treatment effect on abdominal pain, and dose response of MD-7246 administered orally to patients with diarrhea-predominant irritable bowel syndrome (IBS-D). An exploratory objective of the study is to assess bowel function changes with MD-7246 in patients with IBS-D.

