3.2. Discussion of Study Design, Including Choice of Control Group

A double-blind, placebo-controlled, parallel-group study design was chosen in accordance with the concepts in ICH E10, Choice of Control Groups and Related Issues in Clinical Trials, in order to provide comparable treatment groups and minimal chance of selection or investigator bias. The study has a 14-21 day Pretreatment Period to establish patient baseline values without study drug and to familiarize patients with data collection methodology (ie, eDiary), a 12-week Treatment Period to compare the test treatment to a placebo control, and a 2-week Posttreatment Period to assess safety after MD-7246 treatment has been withdrawn.

The study will evaluate the effect of the test treatment on abdominal pain in IBS-D patients. Because the test treatment is not expected to significantly affect bowel function, loperamide will be provided beginning at the Screening Visit for patients to use as needed, at the patients' discretion, to stabilize their diarrhea throughout the study; utilization of loperamide for diarrhea will be recorded on an event-driven basis.

Three doses of MD-7246 were selected to assess the relationship between dose and response.

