4. DETERMINATION OF SAMPLE SIZE

In a previously conducted Phase 2b trial utilizing MD-7246 (ie, Study MCP-103-204), the observed sample standard deviation (SD) for the change from baseline to Week 12 in abdominal pain at its worst ranged from 2.32 to 2.88. Assuming a clinically meaningful treatment difference between MD-7246 and placebo of 1.0 for the mean change from baseline to Week 12 in abdominal pain at its worst, an SD of 2.4, and 92 patients per treatment group (368 patients total), the estimated power is approximately 80% to detect a difference between each MD-7246 dose and placebo at a 2-sided significance level of 0.05 using a 2-sample t-test.

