7.8.9. Efficacy Endpoints and Analyses

All efficacy analyses will be based on the mITT Population, unless otherwise specified. All hypothesis testing will be performed pairwise without adjustment for multiplicity, unless otherwise specified.

Baseline values for efficacy and exploratory parameters are derived from the eDiary and eCRF data collected in the Pretreatment Period, specifically, the period of time from 14 days prior to Randomization Visit and up to the time of the first dose of study drug.

- For patient symptom parameters (eg, abdominal symptoms [pain, bloating, discomfort, cramping]), the baseline value will be the average of the non-missing severity scores reported during the 14-day prior to the first dose during Pretreatment period and up to time of first dose of study drug.
- The baseline BM and urgent BM weekly rates will be derived based on the number of BMs and urgent BMs a patient had during the 14-day prior to the first dose in Pretreatment Period and up to time of first dose of study drug.
- Baseline BSFS score and stool consistency will be calculated as the average of the non-missing values reported by the patient during the 14-day prior to the first dose in Pretreatment Period and up to time of first dose of study drug.

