7.8.9.2. Analyses of the Key Efficacy Endpoints

Change from Baseline in Abdominal Pain Through the Treatment Period

The overall treatment effect will be evaluated via the comparison between the MD-7246 dose groups and placebo with regard to the weekly change from baseline (CFB) in abdominal pain using a MMRM model, including the weekly CFB score in abdominal pain as dependent variable and treatment, visit week (categorical), and treatment-by-week as fixed effects, patient as a random effect, and the baseline value as a continuous covariate. An unstructured covariance matrix will be used for the MMRM analysis, unless the model does not converge, in which case the compound symmetry will be used.

In this MMRM, a patient in mITT population without any postbaseline abdominal pain score at its worse will be considered missing. For patients with postbaseline abdominal pain scores, at any particular week, if there are fewer than 4 daily scores available, the weekly change from baseline will be considered as missing. Weeks after the treatment discontinuation will be considered as missing.

Descriptive statistics for the overall treatment effect based on the MMRM model will include the least-squares (LS) mean difference between each MD-7246 dose and placebo, LS mean change from baseline for each treatment, their corresponding 95% CIs, and the p-values associated with the comparisons to placebo. In addition, LS Means for the weekly treatment differences between each MD-7246 group and placebo will also be provided with the same set of statistics derived from the same MMRM model defined above and will be plotted based on the MMRM estimates.

Additionally, the non-model based descriptive statistics for the corresponding change from baseline (overall or weekly) will be provided by treatment group in the same tables for the MMRM estimates. Among them, the overall change from baseline is defined as the average of all non-missing post baseline daily scores during the Treatment Period minus the baseline abdominal pain score. The cumulative distribution for the overall change from baseline during the entire treatment period will be summarized and plotted by treatment group.

6/12 Week Abdominal Pain 30% Responder

For the 6/12 Week Abdominal Pain 30% Responder endpoint, the proportion of responders in each MD-7246 treatment group will be summarized and compared to the proportion of responders in the placebo group using a CMH test. The number and percentage of responders,

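### Dose response is a stated objective and the reason for three doses, but no efficacy or bowel-function analysis in the SAP uses the dose order or estimates a difference between active doses

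*SAP*

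**What the plan says.** The title calls the trial a "Parallel-group, Dose-range-finding Study of MD-7246 Administered Orally for 12 Weeks". Protocol Section 4 names among the objectives "treatment effect on abdominal pain, and dose response of MD-7246 administered orally", and SAP Section 2 repeats this. In both documents only the bowel-function objective is labelled exploratory.

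On the design, SAP Section 3.2 says: "Three doses of MD-7246 were selected to assess the relationship between dose and response". Protocol Section 7.4 is narrower. It bases dose selection on safety, tolerability and nonclinical models, and says that the 600 and 1200 µg steps were added "to allow for evaluation of dose response in efficacy".

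On the analysis, SAP Section 7.8.9 sets the rule: "All hypothesis testing will be performed pairwise without adjustment for multiplicity, unless otherwise specified". For the first key endpoint, Section 7.8.9.2 lists as output the difference of each dose from placebo, together with "LS mean change from baseline for each treatment, their corresponding 95% CIs, and the p-values associated with the comparisons to placebo". The sample size follows the same logic: "the estimated power is approximately 80% to detect a difference between each MD-7246 dose and placebo" (SAP Section 4).

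**The concern.** A dose-range-finding trial needs a stated way to answer its dose-response question. Here the question would be judged after unblinding from three separate comparisons with placebo. The plan gives no estimate or interval for 600 versus 300 µg, 1200 versus 300 µg or 1200 versus 600 µg, and no ordered analysis. Whoever reads the results would have to choose afterwards what counts as dose response. Differences between active doses, which bear directly on choosing among them, would have to be computed post hoc.

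**Working it through.** **1. Is there an ordered or dose-versus-dose analysis anywhere?**

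| Analysis | Place in SAP | Comparison |
|---|---|---|
| MMRM, change in abdominal pain | 7.8.9.2 | each dose v placebo; treatment categorical, no dose score |
| CMH, 6/12 Week 30% Responder | 7.8.9.2 | each dose v placebo |
| CMH, additional responder endpoints | 7.8.9.4 | active v placebo |
| Poisson or negative binomial, pain-free days | 7.8.9.4 | each arm v placebo |
| MMRM, bowel-function endpoints | 7.8.10 | as for abdominal pain |
| Poisson or negative binomial, urgent BMs and loperamide days | 7.8.10 | active v placebo |

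The proviso in Section 7.8.9 that allows for other specifications is never used to add an ordered analysis. SAP Appendix 1 adds responder endpoints but nothing on dose response. Protocol Section 10.4.2 is also dose versus placebo. SF-12v2 and EQ-5D-3L go to a separate plan that was not supplied, so nothing is said about them here.

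**2. The plan's own figure.** Inputs from SAP Section 4: difference 1.0, SD 2.4, 92 per arm, two-sided 0.05, two-sample t-test. SE = 2.4 × √(2/92) = 0.354; noncentrality = 1.0/0.354 = 2.83; power with 182 df = 80.3%. The stated figure of about 80% reproduces.

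**3. Precision between active doses.** Half-width = 1.967 × SD × √(2/92), using the t quantile for 364 df.

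- SD 2.40: 0.70 points.
- SD 2.32 and 2.88 (the range from the earlier trial): 0.67 and 0.84.

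These SDs are Week 12 values, whereas the planned overall effect averages 12 weeks. If the between-week correlation is ρ, with equal weekly SDs, the SD of the average is 2.4 × √((1 + 11ρ)/12). For an assumed ρ of 0.5 to 0.9 this is 1.77 to 2.29, and the half-width is 0.51 to 0.66.

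**4. A single trend contrast.** Scores −3, −1, 1, 3 for placebo, 300, 600 and 1200 µg. The sum of squares is 20, so SE = 2.4 × √(20/92) = 1.119, with 364 df. The shapes are assumptions, written as benefit over placebo at 300/600/1200 µg. Power is for the beneficial direction.

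| Assumed shape | Contrast value | Value/SE | Power |
|---|---|---|---|
| Linear 0.25/0.5/1 | −0.25 + 0.5 + 3 = 3.25 | 2.90 | 82.6% |
| Step 0/0/1 | 3.00 | 2.68 | 76.2% |
| Plateau 1/1/1 | −1 + 1 + 3 = 3.00 | 2.68 | 76.2% |
| 0.5/1/0.5 | −0.5 + 1 + 1.5 = 2.00 | 1.79 | 43% |
| 0.5/1/0 | −0.5 + 1 = 0.50 | 0.45 | 7% |
| 1/0.5/0 | −1 + 0.5 = −0.50 | −0.45 | 1% |

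For the linear shape, power is 85.0% at SD 2.32 and 67.5% at SD 2.88. Step and plateau give the same contrast value, so this test cannot tell them apart.

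**5. What the pairwise tests show under the same shapes** (simulation). Significance at 1200 µg only occurs in 49% of trials under linear and about 74% under step. All three doses are significant in 62% under plateau and 7% under linear. Under the three non-monotone shapes at least one comparison is significant in 83–84% of trials. With no effect at any dose, that chance is 12.5%.

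**The case against.** The strongest reply is that the objective is to evaluate dose response, not to test it. The SAP supplies LS means by dose with 95% CIs, weekly plots, cumulative distributions, a responder bar plot and a forest plot, and Appendix 1 calls the trial hypothesis generating. That stands in part: a descriptive reading is possible and no formal test is promised. But none of those outputs is an interval for a difference between active doses, and the hypothesis-generating remark is the reason given for dropping sensitivity analyses. It does not withdraw the objective.

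A second reply is that a trend contrast says less about shape than the pairwise tests do. This is correct. The pairwise pattern separates plateau from linear (62% against 7% for all three significant), while the contrast has similar power under all three shapes.

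A third is that power does not improve. This also stands: 1200 µg against placebo alone has about 80% when the top-dose effect is 1.0.

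A reader might go further and infer that the pairwise plan cannot address dose response at all, that a trend test would resolve linear versus step, or that the unadjusted testing is itself a defect. The documents and the calculations support none of these. The lack of adjustment is openly declared (SAP Section 7.6), and an added contrast would control only its own error rate, leaving that of the pairwise tests unchanged.

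**Conclusion.** The point holds as a mismatch between a stated objective and the planned analyses. Dose response is a non-exploratory objective and SAP Section 3.2 makes it the reason for three doses, yet no efficacy or bowel-function analysis in the SAP uses the dose order or estimates a difference between active doses. It is a worthwhile, low-cost improvement and does not invalidate the planned comparisons.

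The finding itself rests on reading the two documents. The sizes are illustrative: they take 92 per arm and SD 2.4 from the SAP, use a Week 12 SD for what would be a 12-week analysis, assume complete data, and use assumed response shapes. The most useful figure is the half-width of about 0.70 points. It shows that differences among active doses will be imprecise relative to the planned effect of 1.0, which is a reason to report them with intervals.

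**What to change.** Before unblinding, add to SAP Section 7.8.9.2:

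1. From the planned MMRM, the estimated overall differences 600−300, 1200−300 and 1200−600 µg, each with a 95% CI.
2. One trend contrast across the four overall LS means with scores −3, −1, 1, 3, at two-sided 0.05. State that significance shows a dose-related drug effect with placebo included, and does not show a difference among active doses or a particular curve shape.
3. For the 6/12 Week 30% Responder, the same three active-dose differences in responder rates with 95% CIs, and a trend test with the same scores.

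Keep all pairwise comparisons with placebo.

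The cost is one SAP paragraph, a few contrast statements on a model already planned, and a short addition to the responder tables; no new data or patients are needed. There are two downsides. The contrast has little power for non-monotone curves, so a null result must not be read as no effect; this is one reason to keep the pairwise tests. The active-dose differences will be imprecise, and the report should say so.

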7.8.9.1. Key Efficacy Endpoints

Change from Baseline in Abdominal Pain Through the Treatment Period

The Change from Baseline in Abdominal Pain Through the Treatment Period is defined as the overall change from baseline in the Abdominal Pain through the Treatment Period, which is estimated based on each weekly change from baseline in the abdominal pain score (based on the daily abdominal pain at its worst score) minus the baseline abdominal pain score for patients in the mITT population.

The postbaseline weekly abdominal pain score is the average of the non-missing daily abdominal pain at its worst scores during a week (Weeks 1-12) if there are at least 4 daily scores entered into the eDairy during the week, or will be considered as missing if there are less than 4 daily scores in the week. Weekly change from baseline will be calculated for each week as the weekly score minus the baseline score.

6/12 Week Abdominal Pain 30% Responder

The 6/12 Week Abdominal Pain 30% Responder is defined for patients in the mITT population and is a patient who meets the Weekly Abdominal Pain 30% Responder criteria for at least 6 out of the 12 weeks of the Treatment Period. A Weekly Abdominal Pain 30% Responder is a patient who has a decrease from baseline of at least 30% in the weekly abdominal pain for that week. If a patient did not have an abdominal pain score for at least 4 days in a particular week during the Treatment Period, the patient will not be considered a Weekly Abdominal Pain 30% Responder for that week. For all weeks after the treatment discontinuation, the patient will be considered as non-responder. A patient in mITT population who did not have any post baseline assessment for abdominal pain at its worst will be considered a weekly non-responder for all post baseline weeks, subsequently, will not be a 6/12 week abdominal pain responder.

7.8.9.2. Analyses of the Key Efficacy Endpoints

Change from Baseline in Abdominal Pain Through the Treatment Period

The overall treatment effect will be evaluated via the comparison between the MD-7246 dose groups and placebo with regard to the weekly change from baseline (CFB) in abdominal pain using a MMRM model, including the weekly CFB score in abdominal pain as dependent variable and treatment, visit week (categorical), and treatment-by-week as fixed effects, patient as a random effect, and the baseline value as a continuous covariate. An unstructured covariance matrix will be used for the MMRM analysis, unless the model does not converge, in which case the compound symmetry will be used.

In this MMRM, a patient in mITT population without any postbaseline abdominal pain score at its worse will be considered missing. For patients with postbaseline abdominal pain scores, at any particular week, if there are fewer than 4 daily scores available, the weekly change from baseline will be considered as missing. Weeks after the treatment discontinuation will be considered as missing.

Descriptive statistics for the overall treatment effect based on the MMRM model will include the least-squares (LS) mean difference between each MD-7246 dose and placebo, LS mean change from baseline for each treatment, their corresponding 95% CIs, and the p-values associated with the comparisons to placebo. In addition, LS Means for the weekly treatment differences between each MD-7246 group and placebo will also be provided with the same set of statistics derived from the same MMRM model defined above and will be plotted based on the MMRM estimates.

Additionally, the non-model based descriptive statistics for the corresponding change from baseline (overall or weekly) will be provided by treatment group in the same tables for the MMRM estimates. Among them, the overall change from baseline is defined as the average of all non-missing post baseline daily scores during the Treatment Period minus the baseline abdominal pain score. The cumulative distribution for the overall change from baseline during the entire treatment period will be summarized and plotted by treatment group.

6/12 Week Abdominal Pain 30% Responder

For the 6/12 Week Abdominal Pain 30% Responder endpoint, the proportion of responders in each MD-7246 treatment group will be summarized and compared to the proportion of responders in the placebo group using a CMH test. The number and percentage of responders,

the differences in responder rates between each MD-7246 dose group and the placebo group, the odds ratio relative to placebo, the corresponding 95% CIs, and the associated p-values will be presented.

A bar plot for the percentage of 6/12 week 30% responders will be provided by treatment group based on the summary statistics. A forest plot for the odds ratios between active treatment arms and placebo will be provided with corresponding 95% confidence intervals.

Regarding the weekly 30% responders, the number and percentage of responders will be summarized for each week within Treatment Period, based on the mITT population. A bar plot by treatment group and by week (for Week 1 and Week 12 only) will be provided.

For any week, a patient with fewer than 4 daily scores available will be considered non-responder for that week.

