10.4.2 Key Efficacy Analysis

Comparisons between the MD-7246 dose groups and placebo with regard to the change from baseline in abdominal pain over the Treatment Period will be evaluated employing a MMRM framework with week (categorical), treatment, geographic region, and week-by-treatment fixed effects, patient as the random effect, and baseline value as a covariate. An unstructured covariance structure will be utilized. Descriptive statistics, for the overall Treatment Period effect, based on the MMRM model will include least-squares (LS) mean change from baseline for each treatment, the LS mean difference between each MD-7246 dose and placebo, corresponding 95% CIs, and the p-value associated with the comparison. In addition, weekly treatment differences between each MD-7246 group and placebo will be provided using the same MMRM model defined above.

For the 6/12 Week Abdominal Pain 30% Responder endpoint, the proportion of responders in each MD-7246 group will be compared to the proportion of responders in the placebo group using a Cochran-Mantel-Haenszel (CMH) test controlling for geographic region. The number and percent of responders, the difference in responder rates between each MD-7246 group and the placebo group, the odds ratio relative to placebo, all corresponding 95% CIs, and the p-value associated with the CMH test will be presented.

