10.4.4 Additional Efficacy Analysis

The additional categorical responder (eg, 6/12 Week Abdominal Bloating 30% Responder) and continuous change-from-baseline endpoints will be analyzed utilizing the same methods defined for the key efficacy endpoints in Section 10.4.2. Treatment Satisfaction will be analyzed utilizing an MMRM framework with week (categorical), treatment, geographic region, and week-by-treatment fixed effects, and patient as the random effect. An unstructured covariance structure will be utilized. Pairwise comparisons between each treatment group and placebo will be performed for the overall Treatment Period effect. MMRM-associated statistics, as defined in Section 10.4.2 for the key efficacy change-from-baseline endpoint, will be presented.

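### The key MMRM places a random patient effect on top of an unstructured covariance, one parameter too many, and so adds an avoidable route to the compound-symmetry fallback

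*SAP*

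**What the plan says.** SAP 7.8.9.2 lists the terms of the key MMRM: treatment, week and their interaction as fixed effects, then "patient as a random effect, and the baseline value as a continuous covariate. An unstructured covariance matrix will be used for the MMRM analysis". If that model fails to converge, compound symmetry takes its place. The SAP does not say that the random effect is dropped in either case. It does not define non-convergence and names no structure between unstructured and compound symmetry.

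Protocol 10.4.2 has the same pairing, "patient as the random effect, and baseline value as a covariate", followed by "An unstructured covariance structure will be utilized", with no fallback. The Synopsis repeats it. Protocol 10.4.4 (Treatment Satisfaction) reads "week-by-treatment fixed effects, and patient as the random effect. An unstructured covariance structure will be utilized", and 10.4.6 does the same for BM-related Symptom Change.

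The outcome is a weekly score, the "average of the non-missing daily abdominal pain at its worst scores during a week (Weeks 1-12"), so each patient contributes up to 12 repeated values. Both the overall treatment effect and the weekly differences from placebo come from this one model. SAP 7.8.9.4, 7.8.10 and 7.8.12 analyse other endpoints with a similar MMRM, so the wording carries over. SAP 7.8.9.3 plans no sensitivity analysis of the key endpoints.

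**The concern.** A random patient intercept adds the same constant to every element of the within-patient covariance matrix. An unstructured matrix can already take any such value, so the intercept variance has nothing of its own to estimate. Compound symmetry is itself a random intercept plus independent error (for non-negative correlation), so a patient effect on top of it is again redundant.

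A flat direction in the likelihood can show up as a zero variance estimate, a warning about the Hessian or the random-effects matrix, or a failure to converge. The SAP makes the last of these the switch to a different covariance model, and does not say whether the others count. Two programmers could follow the same text and report different analyses. The covariance model of a key endpoint should change only because the data cannot support it, not because of how the model was written down. With no sensitivity analysis planned, nothing else in the SAP would show whether the switch mattered.

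**Working it through.** **Plan's own figure.** The documents give no figure for the covariance model. The one related number is the power in SAP section 4: difference 1.0, SD 2.4, 92 per arm, 2-sided 0.05. The standardised difference is 1.0 / (2.4 x sqrt(2/92)) = 2.826, and the power is 80.7% (normal) or 80.3% (t, 182 df), against the stated 80% or so. It rests on a 2-sample t-test at Week 12, so this point does not affect it.

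**Parameter count (exact, no assumptions about the trial).** Write the within-patient covariance as V = R + s x J, where R is the residual matrix, J is a 12 x 12 matrix of ones and s is the patient variance.
- Distinct elements of V: 12 x 13 / 2 = 78.
- Unstructured R plus s: 78 + 1 = 79 parameters; the map to V has rank 78.
- Compound-symmetric R plus s: 2 + 1 = 3 parameters; rank 2.
- Unstructured R alone: 78 parameters, rank 78.

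Each model as written has exactly one parameter too many. Moving s and subtracting the same amount from every element of R leaves V unchanged.

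**Likelihood check.** For 368 simulated patients (assumed SD rising from 1.6 to 2.4, AR(1) correlation 0.9, complete data), the log-likelihood was -5875.617 at s = 0, 0.54, 1.08 and 1.94, with R positive definite each time. The treatment estimates depend only on V, which stays identified.

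**Does the literal model fail to converge?** The 79-parameter model was fitted by maximum likelihood to ten simulated datasets (368 patients, four arms, SD 1.6 to 2.4, AR(1) 0.85, complete data). All ten converged, with s between 1.4 and 1.9. The log-likelihood agreed with the 78-parameter model to within 1e-7 and V to within 4e-5. These fits were not in SAS, which SAP 7.1 names, and had no dropout.

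**If the fallback is used.** The SDs by week and the correlations are not in the documents. Assumed: Week 1 SD between 1.2 and 2.4, moving linearly to 2.4 at Week 12; AR(1) correlation 0.8 to 0.95; no baseline adjustment.
- *Overall effect, complete data.* Compound symmetry uses the mean variance and mean covariance, so the sum of all elements of V is preserved and the ratio of model-based to true standard error is 1.000.
- *Week 12, complete data.* The ratio is sqrt(mean of the 12 variances) / 2.4, and the actual size of a nominal 5% test is 2 x (1 - Phi(1.96 x ratio)):

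| Week 1 SD | Mean variance | Ratio | Actual size |
|---|---|---|---|
| 1.2 | 3.382 | 0.766 | 13.3% |
| 1.6 | 4.063 | 0.840 | 10.0% |
| 2.0 | 4.856 | 0.918 | 7.2% |
| 2.4 | 5.760 | 1.000 | 5.0% |

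- Early weeks go the other way: with Week 1 SD 1.2, the Week 1 ratio is sqrt(3.382) / 1.2 = 1.53, so that standard error is too large.
- *With an assumed 20% monotone, completely random dropout:* actual size 5.2% to 5.6% for the overall effect and 5.9% to 14.6% at Week 12.

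**The case against.** The phrase may be loose wording. Each document names one covariance matrix, and neither mentions an intercept variance or a second covariance component. Patient as a random effect could simply mean that patient is the unit whose weekly scores share that matrix. On that reading there are 78 parameters and no defect. The reading is plausible, but the SAP governs the programming and lists patient as a model term beside the fixed effects, so it should say what it means.

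A reader might infer that the key analysis cannot be estimated, or that the trial will be pushed onto compound symmetry. The documents support neither. Only the split between s and R is unidentified; means, differences, intervals and p-values are the same for a given degrees-of-freedom method, which the SAP does not name. A flat ridge does not imply non-convergence, as the ten fits show, and a Hessian warning is not in itself the SAP's trigger. Those fits do not rule out failure in SAS with incomplete data, so non-convergence remains a possibility of unknown probability.

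Two further points stand. The key endpoint in SAP 7.8.9.1 is the overall change, which the switch barely affects in the scenarios computed. And the Week 12 distortion comes from compound symmetry itself, so it would remain if a real data problem triggered the fallback. The protocol sections have no fallback, so there the matter is only the redundant term.

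**Conclusion.** The specification is wrong as written, and the consequence is conditional. The over-parameterisation by one, in both the main model and the fallback, is exact if the text is taken literally. If the software converges, the reported results are those of the ordinary unstructured MMRM. If it does not, the analysis moves to compound symmetry partly because of the specification. The overall effect then stays close to nominal (5.2% to 5.6% with the assumed dropout). Week 12 tests could run at about 5% to 13% with complete data, or up to 14.6% with that dropout. These sizes rest on assumed SDs, AR(1) correlations and completely random dropout; outcome-dependent dropout was not examined. The correction is worth making because it removes an avoidable route to a worse covariance model for the key endpoint and every analysis that borrows this model.

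**What to change.** In SAP 7.8.9.2, delete the random patient effect from the list of model terms. State that within-patient correlation is modelled only through the residual covariance, with patient as the repeated-measures subject and no separate random effect, in both the unstructured model and the compound-symmetry fallback. Say that this applies to every MMRM that refers to it (SAP 7.8.9.4, 7.8.10 and 7.8.12), and record the departure from Protocol 10.4.2, 10.4.4 and 10.4.6 in SAP Appendix 1. The fallback can then be triggered only by the data. One added sentence defining non-convergence would help. The cost is a few lines of text, with no effect on data collection, patients, sample size or power.
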